3. INVESTIGATIONAL PLAN

3.1. Overall Study Design and Plan

This is an international, multicenter, open-label, long-term safety study of ZX008 in patients with epileptic encephalopathy, including Dravet syndrome or Lennox-Gastaut syndrome. Subjects eligible for participation are those with Dravet syndrome who are currently enrolled in Study ZX008-1503, or those with Lennox-Gastaut syndrome who have successfully completed Study ZX008-1601-Part 2, and are candidates for continued treatment with ZX008 for an extended period of time, or those with Dravet syndrome, Lennox-Gastaut syndrome, or another epileptic encephalopathy who have completed participation in another Zogenix-sponsored study and have been invited to participate in this study.

Subjects having transitioned from ZX008-1503, ZX008-1601 or who have participated in another Zogenix-sponsored study will be eligible to participate in this trial until approval of ZX008 has been obtained from regulatory authorities for the subject's indication, until a managed access program is established as allowed per country-specific requirements in addition to legal and regulatory guidelines in the subjects country of residence, or until the investigational product development for the subject's indication is stopped by the Sponsor, whichever comes first.

All subjects who discontinue from the study treatment and do not transition directly to commercial product will undergo up to 2-weeks taper of study medication. (Note subjects enrolled in the United Kingdom will have an additional follow-up safety visit 12 months after the last dose; subjects enrolled in Germany, France, and Netherlands will have an additional follow-up safety visit at 24 months after the last dose).

Subjects entering this OLE study who have participated in 1503 or 1601 will receive ZX008 initially at the dose prescribed at the last visit in Study 1503 or Study 1601 Part 2, but will have the volume adjusted according to weight of the patient. Dose increases, to a maximum of 0.8 mg/kg/day (maximum 30 mg/day) for subjects not receiving concomitant STP or 0.5 mg/kg/day (maximum 20 mg/day) for subjects receiving concomitant STP, during this OLE study should not occur more frequently than every 7 days in dose increments of not more than 0.2 mg/kg/day. Dose increases (as per mg/kg) may only occur after a review of reported adverse events (AEs), and if, in the investigator's opinion, seizure frequency, severity, or duration indicates a change in medication regimen is warranted. Dose decreases for tolerability or safety concerns can occur at the investigator's discretion, in dose amounts and frequency appropriate for the clinical situation. ZX008 dose adjustments outside of these parameters should be discussed with the CRO Medical Monitor prior to initiation.

Changes in dosage of concomitant AEDs may be implemented as clinically necessary, and concomitant AEDs may be withdrawn completely, but all subjects must remain on a minimum of 1 concomitant AED plus ZX008 unless it is deemed clinically appropriate by the investigator (after discussion with the CRO Medical Monitor) to dose as monotherapy. New concomitant AEDs or anti-epileptic treatments may be introduced at the investigator's discretion, as would be typically indicated in clinical practice. Clinical worsening leading to a change in medication must be documented in the source notes and case report form (CRF) and all medication dose

Confidential Page 29 of 105

22 September 2022

changes must be documented with a clinical explanation and justification. Any addition of a new AED must be discussed with the CRO Medical Monitor prior to implementation.

Echocardiograms (ECHO) and other safety assessments detailed in the schedule of assessments (SoA) will be conducted every 6 monthsunless more frequent follow-up is clinically indicated or required by the Sponsor or IDSMC. A follow-up visit and a cardiac safety assessment will be performed after study drug discontinuation for subjects who do not transition to commercially available ZX008. Subjects who transition to commercially available ZX008 will not return for a follow-up after EOS/ET or a cardiac follow up after last dose but must have had an ECHO within 3 to 6 months before the transition date and will have follow-up ECHOs within required timeframe while on commercial drug supply.

Caregivers will be asked to use a diary to record the number/type of seizures to support investigator determination of treatment benefit; however, diary data collection is not mandatory, nor will it be collected in the database. A schedule of assessments is provided in Table 1.

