5.4.2. Taper Period

All subjects (those who complete the OLE Treatment Period and those who discontinue from the study early) will be tapered off of study medication.

The tapering scheme is a 2-step process as described in Table 3.

Study medication will be administered as equal doses BID in the morning and in the evening, approximately 12 hours apart. Each dose should be separated by a minimum of 8 hours and a maximum of 12 hours. A missed dose of study medication may be taken later up to 8 hours

Confidential Page 41 of 105

22 September 2022

before the next scheduled dose; otherwise, the missed dose should not be given. IMP will be administered using the oral dosing syringe provided.

Taper Algorithm Table 3.

Current Dose	Taper Step 1 Days 1-4 after study completion or early termination	Taper Step 2 Days 5-8 after study completion or early termination
ZX008 0.2 mg/kg/day	Not applicable	Not applicable
ZX008 0.4 mg/kg/day	ZX008 0.2 mg/kg/day	Not applicable
ZX008 0.5 mg/kg/day (for subjects taking concomitant STP)	ZX008 0.4 mg/kg/day	ZX008 0.2 mg/kg/day
ZX008 0.6 mg/kg/day	ZX008 0.4 mg/kg/day	ZX008 0.2 mg/kg/day
ZX008 0.8 mg/kg/day	ZX008 0.4 mg/kg/day	ZX008 0.2 mg/kg/day
Note: maximum daily dose	of ZX008 is 30 mg (or 20 mg for subjects taki	ng concomitant STP).

5.5.

This is an open-label study.

5.6.

Prior and Concomitant Medication

tions taken by a subject after the first administration

t medication and herbol All medications taken by a subject after the first administration of IMP in this study, and those that started before the first administration of IMP and are continuing, are regarded as concomitant medication and must be documented in the eCRF, including over-the-counter medication, herbal and vitamin/supplement preparations.

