6.1.3. Clinic Visit 7 (Month 36): End of Study/Early Termination

The End-of-Study participation for an individual subject occurs when approval of ZX008 has been obtained from regulatory authorities for the subject's indication, when a managed access program is established as allowed per country-specific requirements in addition to legal and

Confidential Page 47 of 105

22 September 2022

regulatory guidelines in the subjects country of residence, or when the investigational product development for the subject's indication is stopped by the Sponsor, whichever comes first. In that regard, participation could be extended beyond 36 months if none of the conditions above mentioned are met at Visit 7.

. The End-of-Study visit may also occur if the subject withdraws participation from the study. Subjects will visit the clinic for the End-of-Study Visit if 1 the following events occur:

- 1. The subject withdraws or is withdrawn from participation in the study.
- 2. The Sponsor terminates the study.
- 3. The subject completes all study related visits and procedures.
- 4. ZX008 is approved by regulatory authorities for the subject's indication, a managed access program is established as allowed per country-specific requirements in addition to legal and regulatory guidelines in the subjects country of residence, or the investigational product development for the subject's indication is stopped by the Sponsor, whichever comes first.

The following procedures will be performed:

- Record concomitant medications
- Abbreviated physical examination, as clinically indicated. A full physical and/or neurological examination may be performed, if warranted. Abnormal clinically significant findings must be reported as adverse events.
- Abbreviated neurological examination, as clinically indicated. A full physical and/or neurological examination may be performed, if warranted. Abnormal clinically significant findings must be reported as adverse events.
- Height and weight, and calculation of BMI
- Obtain vital signs
- ECG, as clinically indicated (conducted and read locally). Abnormal clinically significant findings must be reported as adverse events.
- Doppler ECHO
- Chest X-ray (in France and Netherlands only), as clinically indicated, Abnormal clinically significant findings must be reported as adverse events.
- EEG (in Italy only), as clinically indicated, Abnormal clinically significant findings must be reported as adverse events.

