6.3. Cardiac Follow Up Visit (Clinic Visit 9; last dose + 6 Months)

If the subject completes the study (or discontinues from the study early), and is not switching to commercially available drug, the subject will visit the clinic 6 months after the last dose. At the 6 month follow up visit, the following procedures will be performed, with additional follow-ups based on country of residence (see table 5).

- Abbreviated physical/neurological examination. A full physical and/or neurological examination may be performed, if warranted. Abnormal clinically significant findings must be reported as adverse events.
- 12-lead ECG (conducted and read locally)
- Doppler ECHO
- Record AEs
- Record concomitant medications

If the subject completes the study or discontinues from the study early, the subject will return to the clinic for follow-up cardiac testing (ECHO, ECG, and in some cases, physical examination). The timing and frequency of exams are in Table 5. As the ECHO and ECG will be administered

Confidential Page 49 of 105

in a separate clinic than the pediatric neurology clinic, an asymptomatic subject receiving a second follow-up ECHO and ECG does not require a physical examination.

Subjects with positive findings on ECHO, ECG and/or physical examination should continue to be followed until the finding is resolved or stable and unlikely to change, with reports submitted as AEs to the ZX008 safety database.

If the subject completes the study (or discontinues from the study early) and is switching to commercially available drug, the subject will complete the EOS visit and follow the drug administration process outlined for commercial product as advised by the subject's physician. The EOS/ET and cardiac follow-up visits are not required.

Schedule of Post-Treatment Cardiac Follow-up Table 5.

The EOS/ET and card	liac follow-up visits are not requir	ed.
Table 5. Sched	ule of Post-Treatment Cardiac F	Tollow-up
Parameter		Have had any clinically significant cardiac sign or symptom regardless of the time on study drug ^a
ECHO and ECG	Follow-up 6 months post-treatment ^b in UK: additional 12-month follow-up in Germany, France, Netherlands: additional 24-month follow-up	Follow-up 6-24 months post-treatment ^b , and every 6 months until resolved, or stable and unlikely to change

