7.6.3 Open-label Extension (OLE) Treatment Period

The OLE Treatment Period covers the period during which subjects will receive open label treatment with ZX008 until approval of ZX008 has been obtained from regulatory authorities for the subject's indication and country of residence, until a managed access program is established, or until the investigational product development for the subject's indication is stopped by the Sponsor, whichever comes first.

7.6.4 **Post-dosing Period**

For subjects discontinuing from study treatment and not transitioning to commercial drug, the Post-dosing Period begins immediately at the end of OLE Treatment Period defined by EOS/ET Study Visit and extends for a planned 2 weeks. This includes the Taper Period, if applicable to

Zogenix International Limited, a wholly owned subsidiary of UCB 27 October 2023 Statistical Analysis Plan Fenfluramine Hydrochloride ZX008-1900/EP0215 the subject. The visit at the end of the Post-dosing Period is labelled "EOS/ET +14 days" in

outputs.

7.6.5 **Mean Daily Dose**

The mean daily dose for a subject, sometimes referred to as the actual mean daily dose, is the average dose of ZX008 in mg/kg/day taken by a subject between Visit 1 and the EOS/ET Visit.

The calculation of the mean daily dose is based on the actual dose of ZX008 and takes into account dosing rules that capped the amount of drug that could be taken in a single day.

The mean daily dose of ZX008 per subject during the OLE is calculated from the weighted average of the assigned daily dosages by the investigator during the study, and the number of days the subject was maintained at each dose level.

The following categories will be used to describe mean daily dose and will be presented in mg/kg/day:

• 0 - < 0.4• 0.4 - < 0.6• ≥ 0.6 On each day, the actual dose will be calculated as:

On each day, the actual dose will be calculated as:

- 1. Assigned dose level (mg/kg), if the subject's weight (kg) * assigned dose (mg/kg) was ≤ Maximum allowed dose or
- 2. 30 (mg) / weight (kg), if the subject's weight (kg) * assigned dose (mg/kg) was > Maximum allowed dose, if the subject was not on concomitant STP or
- 3. 20 (mg) / weight (kg), if the subject was on concomitant STP and the subject's weight (kg) * assigned dose (mg/kg) was > 20 mg.

The reasoning for this is that the maximum quantity to be given on any day is 30 mg for subjects not on concomitant STP and 20 mg for subjects on concomitant STP.

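### Managed access is a planned way to leave the study, but the taper, follow-up, post-dosing and completion rules recognise only a move to commercial drug

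*Protocol*

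**What the plan says.** **End of participation.** Protocol 3.1 lets subjects take part until approval for their indication, "until a managed access program is established as allowed per country-specific requirements in addition to legal and regulatory guidelines", or until the sponsor stops development, whichever is first. Protocol 6.1.3 repeats this (participation ends "when a managed access program is established as allowed per country-specific requirements") and lists the same trigger among the events that require the End-of-Study visit.

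**Intent.** Protocol 1.6 gives the study's main purpose as continuing to supply treatment until one of these events. SAP 7.6.7 allows a subject to stay beyond 36 months when the drug is not yet approved and no managed access programme is available to that subject.

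**Taper.** In Protocol 3.1, subjects who stop study treatment and "do not transition directly to commercial product will undergo up to 2-weeks taper of study medication". The synopsis and 3.3 agree. Protocol 5.4.2 has no exemption: "All subjects (those who complete the OLE Treatment Period and those who discontinue from the study early) will be tapered off of study medication". SAP 4.6.2 exempts only a move to commercial product where it is approved.

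**Follow-up.** Protocol 3.1 says that the follow-up visit and cardiac assessment "will be performed after study drug discontinuation for subjects who do not transition to commercially available ZX008". Under Protocol 6.3, unless switching to commercial drug, "the subject will visit the clinic 6 months after the last dose". Section 6.2 and Table 1 footnote h use the same single exemption.

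**Analysis.** SAP 7.6.4 opens: "For subjects discontinuing from study treatment and not transitioning to commercial drug, the" Post-dosing Period starts at the EOS/ET visit and runs a planned two weeks. SAP 7.6.7 defines completion as 36 months of treatment (24 in Denmark) or transition to commercial drug.

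**The concern.** The list of reasons to leave has three entries, but the rules for what happens next recognise one continuing route, commercial supply. A subject who leaves because managed access has begun belongs to a route that the protocol itself plans, and falls by default under the rules for people coming off the drug.

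Two things are at stake. A site following the text would taper an anti-seizure drug in a subject whom the trigger implies will continue it, and would book post-treatment visits. In the analysis, the same subject enters the Post-dosing Period and, if the exit is early enough, counts as not having completed a study that ended for them as planned.

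**Working it through.** The plan gives no figure to reproduce. The check sets the exit rules beside the rules that follow from them.

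**Step 1: does any rule name managed access as a continuing route?**

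| Rule | Place | Who is exempt |
|---|---|---|
| Taper | Protocol synopsis, 3.1, 3.3 | commercial transfers |
| Taper | Protocol 5.4.2 | nobody |
| Taper | SAP 4.6.2 | commercial transfers where approved |
| 14-day visit | Protocol 3.1, 6.2, Table 1 footnote h | commercial transfers |
| 6-month cardiac visit | Protocol 3.1, 6.3, Table 1 footnote h | commercial transfers |
| Post-dosing Period | SAP 7.6.4 | commercial transfers |
| Counted complete before 36 months (24 in Denmark) | SAP 7.6.7 | commercial transfers |

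Managed access appears in none of them. The 5.4.2 row also conflicts with the 3.1 row for commercial transfers.

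**Step 2: could commercial product be read to include managed access?** Neither document says so. SAP 4.6.2 ties commercial product to places where it is approved, while the protocol lists approval and managed access as separate events.

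**Step 3: could a managed-access subject escape because they have not discontinued?** The taper rule in 3.1 and the period in SAP 7.6.4 first require that study treatment is discontinued. If continuing ZX008 from another supply did not count as discontinuing, commercial transfers would need no exemption, yet they are given one. Protocol 6.2 and 6.3 apply to completers as well, and 5.4.2 applies to all subjects, so this condition does not help there.

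**Step 4: completion status.** SAP 7.6.7 treats 36 months as reached if the EOS/ET visit is on Study Day 1050 or later. That is 30 days before the planned day: 1080 − 30 = 1050, and for Denmark 720 − 30 = 690.

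- Exit at Month 30 (Day 900) to commercial drug: completed.
- Exit at Month 30 (Day 900) to managed access: 900 < 1050, so not completed, by 1050 − 900 = 150 days.
- Danish exit at Month 18 (Day 540) to managed access: 540 < 690, so not completed, by 690 − 540 = 150 days.

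The last two meet a planned end of participation under Protocol 6.1.3. SAP 9.1 puts completion and discontinuation in the disposition table, and SAP section 14 lists that table as a registry output. With n such exits among N subjects, the completion percentage is lower by n/N. At the stated ceiling of about 650 subjects, each exit moves it by 1/650 = 0.15 percentage points. The documents do not give n.

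**Step 5: likely origin.** Protocol Appendix 7 lists the sections edited when the end-of-participation wording changed: the synopsis, Schedule of Assessments, 1.6, 3.1, 3.3, 6.1.3 and 10.4. Sections 5.4.2, 6.2 and 6.3 are not on that list. This is an inference about how the gap arose; the point does not depend on it.

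**The case against.** The strongest reply is that this is an omission about one exit route, with little analytic effect. Much of that is fair.

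- Protocol 4.4 leaves the choice between stopping at once and tapering to the site investigator, after discussion with the CRO Medical Monitor. Practice may therefore differ from the literal text. This stands, but 4.4 offers no route for continuing through managed access.
- No sentence says outright that managed-access subjects stay on ZX008. This stands; it is inferred from Protocol 1.6 and SAP 7.6.7.
- The Post-dosing Period does little in the SAP. SAP 9.13.2 does not end the treatment-emergent window there, effectiveness summaries use Months 6 to 36 and the last on-treatment visit, and mean daily dose stops at EOS/ET. This stands and limits the consequence.
- Few subjects may be affected. The SAP introduction reports authorisation in the United States, Europe and the United Kingdom for both enrolled indications, and SAP 12.1 says that no Japanese patients will be enrolled. It mentions no authorisation in Australia or Canada, so the number is open.

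A reader might infer more than the text supports:

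- *That the last dose is wrongly moved 8 days later.* SAP 7.6.2 and 9.12.2 add 8 days only when the last-dose date cannot be determined and the subject is tapering. A subject who continues without taper gets the EOS/ET date.
- *That off-drug persistence of cardiac findings becomes unreadable.* The SAP labels the visit simply as a 6-month cardiac follow-up and specifies no persistence or reversal summary. ECHO and ECG analyses are in a separate cardiovascular SAP that is not available here. A figure for the distortion would need invented inputs.
- *That exposure-adjusted event rates are inflated.* This needs a subject who skips the taper, stays on drug and still attends the cardiac visit. The documents do not say that this happens.

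**Conclusion.** The point holds as a contradiction within the protocol and a gap carried into the SAP. The rules as written give a result at odds with the reason for ending participation: managed-access exits are tapered and followed as post-treatment. Protocol 5.4.2 separately contradicts 3.1 for commercial transfers.

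Two consequences in the SAP are supported. Managed-access exits fall in the Post-dosing Period, and those before Day 1050 (690 in Denmark) are non-completers in the disposition table and its registry output. The effect on the completion percentage is n/N, with n not given. Tapering and on-drug follow-up data are alternatives for any one subject: a subject who is tapered as written contributes genuine off-drug data.

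The conclusion rests on reading managed access as a replacement for study supply and commercial product as excluding it. It does not depend on the country-specific amendments, which may say more but are not available here. The correction should be made because it is cheap and the text as it stands can misdirect sites.

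**What to change.** **Protocol.** Reconcile the synopsis (duration of treatment), Table 1 footnote h, and sections 3.1, 3.3, 5.4.2, 6.2 and 6.3. They should say in the same terms whether the taper, the 14-day visit and the 6-month cardiac visit apply to managed-access exits, and 5.4.2 should agree with 3.1 on commercial transfers. Which clinical rule applies is the sponsor's decision.

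**SAP.** Bring 4.6.2, 7.6.4 and 7.6.7 into line with that decision. Derive one flag from the exit reason, continued ZX008 after study (commercial or managed access). Use it in the Post-dosing Period and study-completion definitions, and show any data after EOS/ET from flagged subjects separately. Report the number of managed-access exits in the disposition table so that the size of the issue is visible.

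**Cost.** A clarification letter or amendment wording, and one derived variable before database lock. The documents do not show the exit-reason categories on the CRF; if managed access is not a separate one, a data query will be needed. The downside is slightly fewer subjects in the post-treatment summaries.

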3.2. Number of Subjects

Up to approximately 650 subjects from the core studies may be enrolled. The number of subjects is dependent on the number who participate in Study ZX008-1503 or ZX008-1601 Part 2 and who volunteer for the extension study and meet the necessary criteria for enrollment.

3.3. Study Duration

Subjects having transitioned from ZX008-1503, ZX008-1601 or who have participated in another Zogenix-sponsored study, will be eligible to participate in this trial until approval of ZX008 has been obtained from regulatory authorities for the subject's indication, until a managed access program is established as allowed per country-specific requirements in addition to legal and regulatory guidelines in the subjects country of residence, or until the investigational product development for the subject's indication is stopped by the Sponsor, whichever comes first..

All subjects who discontinue from the study treatment and do not transition directly to commercial product will undergo up to 2-weeks taper of study medication. (Note subjects enrolled in the United Kingdom will have an additional follow-up safety visit 12 months after the last dose; subjects enrolled in Germany, France, and Netherlands will have an additional follow-up safety visit at 24 months after the last dose).

